APPENDIX B

Procedural Guidelines for Loading HepaSphere/QuadraSphere with Doxorubicin (hqTACE)

CAUTION: INVESTIGATIONAL DEVICE in the United States. LIMITED BY UNITED STATES LAW TO INVESTIGATIONAL USE in the United States.

Supplies:

- 3 x doxorubicin 50mg powder vials
- 2 x HepaSphere/QuadraSphere vials
- 20G needles
- 2 x 20mL syringes
- 5 x 30mL syringes
- 4 x 10mL vials 0.9% normal saline for injection
- 2 x syringe caps

Procedure:

****Prepare in Biohazard Hood****

1. Attach a 20g needle to a 30ml syringe containing 20ml of 0.9% normal saline for injection.
 - a. Doxorubicin 50mg vial #1: Reconstitute 1 vial of doxorubicin 50mg with 20mL 0.9% normal saline for injection via the 30ml syringe.
2. Using 2 new 20ml syringes, attach a 20g needle to each (syringe A&B):
 - a. With Syringe A: Withdraw 10mL of the reconstituted doxorubicin from the doxorubicin 50mg vial and set aside.
 - b. With Syringe B: Withdraw the remaining 10mL of reconstituted doxorubicin from the doxorubicin vial and set aside.

**This process should yield 2- 20ml syringes (A&B), each containing doxorubicin 25mg/10ml.*

3. Lift the cap of each (2 vials) HepaSphere/QuadraSphere vial to the vertical position taking care NOT to remove the cap or the metal retaining ring from the vial.
4. Roll each vial several times to disperse the microspheres within their respective vial.
5. With syringe A:
 - a. Attach a new 20g needle to a syringe containing 10ml of solubilized doxorubicin.
 - b. Slowly add the 10mL of doxorubicin to one of the HepaSphere/QuadraSphere vials by puncturing the grey stopper with the 20g needle and allowing the contents to naturally aspirate from the syringe into the vial.
6. Gently rotate and invert the HepaSphere/QuadraSphere vial back and forth so that the liquid contacts the grey stopper 5 to 10 times.

7. With syringe B:
 - a. Attach a new 20g needle to the other syringe containing 10ml of solubilized doxorubicin.
 - b. Slowly add the 10mL of doxorubicin to the remaining HepaSphere/QuadraSphere vial by puncturing the grey stopper with the 20g needle and allowing the contents to naturally aspirate from the syringe into the vial.

8. Gently rotate and invert the HepaSphere/QuadraSphere vial back and forth so that the liquid contacts the grey stopper 5 to 10 times.

**This process should yield 2-HepaSphere/QuadraSphere vials each containing doxorubicin 25mg/10ml.*

9. Set the HepaSphere/QuadraSphere vials containing the 10ml of doxorubicin aside and allow the vials to stand for a minimum of 10 minutes.

While waiting:

10. Reconstitute the remaining 2 doxorubicin 50mg vials with 20ml of 0.9% normal saline for injection in each vial:
 - a. doxorubicin 50mg vial #2- Utilizing a new 30ml syringe with a 20g needle attached, inject 20ml of 0.9% normal saline for injection.
 - b. doxorubicin 50mg vial #3- Utilizing a new 30ml syringe with a 20g needle attached, inject 20ml of 0.9% normal saline for injection.

**This process should yield two doxorubicin 50mg vials each with 10ml of 0.9% normal saline.*

11. Using 2 new 30ml syringes, each with a 20G needle attached (syringe C&D):
 - a. With Syringe C: Withdraw the entire 10mL of reconstituted doxorubicin from one of the doxorubicin vials (50mg) and set aside.
 - b. With Syringe D: Withdraw the entire 10mL of reconstituted doxorubicin from the other doxorubicin vial (50mg) and set aside.

**This process should yield two 30ml syringes each containing doxorubicin 50mg/10ml.*

After the 10 minutes in step 9:

12. Utilizing syringes C&D from step 11:
 - a. Syringe C: Attach a 20g needle to the 30ml syringe containing the doxorubicin 50mg/20ml and aspirate the contents (doxorubicin loaded spheres) of one HepaSphere/QuadraSphere vial into the 30ml syringe containing the doxorubicin 50mg/10ml.
 - b. Syringe D: Attach a 20g needle to the 30ml syringe containing doxorubicin 50mg/20ml and aspirate the entire contents of the remaining HepaSphere/QuadraSphere vial from step 9 into the syringe. (Do not attempt to extract every red colored sphere).
13. Prior to removing the needle from the HepaSphere/QuadraSphere vial, while holding the syringe vertically, gently pull the plunger of the syringe down, removing any solution that may be in the hub of the needle.
14. Remove the needle and cap the syringe.
15. Each syringe should contain a total volume of 30ml.
16. Invert the syringes several times to disperse and mix the contents in the syringe.
17. Record the time that Step 16 was completed.
18. Allow syringe to sit for 60 minutes to complete loading of doxorubicin.

**This process should yield two 30ml syringes, each containing 1 vial of HepaSphere/QuadraSphere loaded with doxorubicin 75mg/20ml.*

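### Appendix B (hqTACE loading) gives conflicting volumes; combining step 10's 20 mL with step 11's 10 mL would leave a full-dose preparation 33% short of doxorubicin

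*Combined protocol and SAP*

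**What the plan says.** Appendix B prepares a full 150 mg load from three 50 mg vials of doxorubicin and two vials of microspheres. Steps 1 to 8 dissolve vial 1 in 20 mL and put half (25 mg in 10 mL) into each microsphere vial. Steps 10 to 18 dissolve vials 2 and 3, draw them into syringes C and D, and take up the contents of one microsphere vial into each syringe.

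The volumes given for this second part are:

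- Supplies: "4 x 10mL vials 0.9% normal saline for injection", which is 40 mL.
- Step 10: "Reconstitute the remaining 2 doxorubicin 50mg vials with 20ml of 0.9% normal saline for injection in each vial". Sub-steps a and b each repeat 20 mL.
- Note after step 10: "This process should yield two doxorubicin 50mg vials each with 10ml of 0.9% normal saline".
- Step 11a: "With Syringe C: Withdraw the entire 10mL of reconstituted doxorubicin from one of the doxorubicin vials (50mg) and set aside". Step 11b says the same for syringe D.
- Note after step 11: "This process should yield two 30ml syringes each containing doxorubicin 50mg/10ml".
- Step 12a describes syringe C in two ways within one sentence: "doxorubicin 50mg/20ml and aspirate the contents (doxorubicin loaded spheres) of one HepaSphere/QuadraSphere vial into the 30ml syringe containing the doxorubicin 50mg/10ml". Step 12b gives 50 mg in 20 mL for syringe D.
- Step 15: "Each syringe should contain a total volume of 30ml".
- Note after step 18: each syringe is "loaded with doxorubicin 75mg/20ml".

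Appendix C (Embolic Preparation, step 1) also gives 20 mL as the volume in the loaded syringe.

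**The concern.** These are current instructions for preparing a cytotoxic dose, and they cannot all be followed. A preparer has to choose between 10 and 20 mL, and the text does not say which figure governs.

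One choice loses drug. A preparer who adds the 20 mL printed in step 10 and then draws the 10 mL printed in step 11 leaves half of vials 2 and 3 behind. The resulting syringe has the final volume that the closing note and Appendix C expect, so a check against either would pass it.

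Section 5 (Study Design) assigns both arms the same dose, 75 mg/m² up to 150 mg per cycle. The control preparation in Appendix D has no such conflict: three vials in 5 mL each make 15 mL, split into two syringes of 75 mg in 7.5 mL. Any error caused by this text would therefore fall on the hqTACE arm only.

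**Working it through.** **Inputs.** Vials 2 and 3 hold 50 mg each. Each microsphere vial already holds 50 × 10/20 = 25 mg in 10 mL (steps 1 to 8). Vial 1 used 20 mL of saline.

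**Formulas.** Let *a* be the diluent added to each of vials 2 and 3, and *d* the volume drawn from each.

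- Drug per syringe = 25 + 50 × *d*/*a* mg
- Final volume per syringe = 10 + *d* mL
- Saline used = 20 + 2*a* mL

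**Results.** The plan's own figure, 75 mg in 20 mL, is reproduced by the first row.

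| Added / drawn | Drug per syringe | Total drug | Final volume | Concentration | Saline used |
|---|---|---|---|---|---|
| 10 / 10 mL | 25 + 50 = 75 mg | 150 mg | 20 mL | 3.75 mg/mL | 40 mL |
| 20 / 20 mL | 25 + 50 = 75 mg | 150 mg | 30 mL | 2.5 mg/mL | 60 mL |
| 20 / 10 mL | 25 + 25 = 50 mg | 100 mg | 20 mL | 2.5 mg/mL | 60 mL |

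The third row leaves 25 mg in each of vials 2 and 3. The shortfall is (150 − 100)/150 = 33%.

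**Which statements fit which row.**

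- 10/10 fits the saline supply, the notes after steps 10 and 11, the second description in step 12a, the closing note and Appendix C step 1.
- 20/20 fits step 10 with its sub-steps, the first description in step 12a, step 12b and step 15.
- 20/10 fits the number in step 10, the number in step 11 and the 20 mL final volume. It fails the instruction in step 11 to take the whole content, every stated drug mass from step 11 onward, step 15 and the saline supply.

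**Cross-check against Appendix C, steps 5 to 7.** The operator discards up to 10 mL of supernatant and adds 10 to 15 mL of contrast, for a stated half-and-half mix.

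- From 20 mL: 20 − 10 = 10 mL left; adding 10 mL of contrast gives 20 mL at 50%.
- From 30 mL: 30 − 10 = 20 mL left; adding 10 to 15 mL gives 30 to 35 mL at 10/30 = 33% to 15/35 = 43%. A true half-and-half mix needs 20 mL of contrast, or 40 mL in a 30 mL syringe.

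This points to 20 mL as the intended final volume. It is an indication only, because the purge is an upper limit and the operator may add more contrast.

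**Who gets a full preparation.** Section 5 rounds the dose up to the next 25 mg, so the dose is 150 mg whenever 75 × body surface area exceeds 125 mg, that is, above 125/75 = 1.67 m². The documents do not give the distribution of body surface area. In bilobar disease the cycle dose is divided between the lobes.

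**The case against.** The strongest reply is that the 33% shortfall is an assembled error and not something the text instructs. Step 11 says to take the vial's entire content, and every later mass (50 mg in syringes C and D, 75 mg at the end) contradicts a half draw. Step 15 would catch it, because the syringe would hold 20 mL instead of 30 mL. The supply list would catch it sooner: after vial 1 only 20 mL of saline remains, enough for 10 mL per vial, so the preparer would have to fetch another 20 mL. Both coherent readings give the full dose. Prepared dose is also not delivered dose, since supernatant is discarded, not every sphere is extracted, and stasis may come before the full load is given. Finally, the documents do not say which volume was validated, and choosing 10 mL changes the loading concentration from 2.5 to 3.75 mg/mL.

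Most of this stands, and it limits the claim: the shortfall is conditional, it concerns the prepared dose, and the intended volume needs the sponsor's confirmation. It does not remove the defect. In step 11 the word *entire* is attached to a figure that contradicts step 10, so the preparer must choose between the word and the number. Steps 2a and 2b have already had the same preparer draw 10 mL portions from a 20 mL vial. Step 15 is itself one side of a conflict, so failing it does not clearly signal an error.

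**Conclusion.** The point holds. Appendix B conflicts with itself, and in part with Appendix C, on four quantities: diluent for vials 2 and 3 (20 or 10 mL), content of syringes C and D (50 mg in 20 mL or in 10 mL), final volume (30 or 20 mL) and saline (60 mL used, 40 mL supplied). Drug mass is stated consistently, and either consistent reading delivers 75 mg per syringe.

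The size of the risk is 50 mg out of 150 mg in a full preparation, and only if the 20 mL addition is combined with a 10 mL draw. It is not a deficit across the arm. The documents do not show that any site made this error or how likely it is, and no effect on survival, response or toxicity is claimed. It should be corrected because the text governs dosing in the experimental arm and the short preparation passes two of the stated volume checks.

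**What to change.** Subject to confirmation by the sponsor's pharmacy team that 10 mL was intended:

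- Step 10 and sub-steps a and b: 10 mL per vial.
- Steps 12a and 12b: 50 mg in 10 mL throughout.
- Step 15: 20 mL.
- Step 11: add that vials 2 and 3 must be empty after withdrawal. This check exposes the short draw whichever volume is confirmed.

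These changes bring Appendix B into line with its own supply list, its yield notes and Appendix C. If 20 mL proves to be the validated volume, the supply list, the notes after steps 10, 11 and 18, the withdrawal volumes in step 11, the second description in step 12a and Appendix C need changing instead.

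The cost is a few corrected figures or a pharmacy clarification memo, with no change to design or analysis. A table of recorded dose by arm and site is optional. It may not reveal past errors, because sites would probably have recorded the nominal dose.

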APPENDIX C

Procedural Guidelines for Embolization with HepaSphere/QuadraSphere loaded with Doxorubicin (hqTACE)

CAUTION: INVESTIGATIONAL DEVICE in the United States. LIMITED BY UNITED STATES LAW TO INVESTIGATIONAL USE in the United States.

Arteriography:

1. Perform routine diagnostic visceral angiography (Aorta, SMA ,Celiac) with delayed portal venous phase.
2. Conduct selective angiography (PHA, LHA, RHA, etc). Perform complete hepatic arteriography, selecting and mapping any accessory or replaced artery as identified.
3. After delineation of the arterial anatomy, advance a coaxial 3 Fr microcatheter with a minimum inner diameter of 0.024" through the guiding catheter.
4. Serially sub-select and map the smallest arterial branches supplying identified tumors.
5. Multiple super selective catheterizations may be necessary.

Catheter placement and aberrant anatomy:

1. Prior to hqTACE, in cases where substantial or clinically relevant arterial portal venous shunting is present, embolize any identified shunts in a manner that occludes the shunt but preserves the hypervascularity of the tumor.
2. Patients with unifocal tumors should undergo selective chemoembolization, in which a 3 Fr microcatheter is placed selectively into a second or third-order branch off the right or left hepatic artery in closer proximity to the tumor.
3. In cases where selective catheterization of second or third-order branches off the right or left hepatic artery is prohibited, segmental catheter position is acceptable.
4. Lobar embolization should be performed only if selective or segmental embolization is not an option.

Embolic Preparation prior to injection:

1. The doxorubicin loaded HepaSphere/QuadraSphere will be contained in up to two 30ml syringes. Each syringe will contain the contents from 1 vial of HepaSphere/QuadraSphere (25mg of embolic) loaded with up to doxorubicin 75mg. The total volume in the syringe will be 20ml.

2. Pass the contents of the 30ml syringe containing the doxorubicin loaded HepaSphere/QuadraSphere into a 30ml syringe within the operative field via a 3-way stopcock.
3. After passing the contents of the doxorubicin loaded HepaSphere/QuadraSphere syringe into the operative field, connect the syringe to an open port on a 3 way-stopcock.
4. Connect an empty 20ml syringe to one of the remaining open ports on the stopcock.
5. Purge up to 10ml of supernatant from the 30ml HepaSphere/QuadrSphere syringe into the 20ml syringe via the 3 way-stopcock. (The supernatant will be pink in color and should be discarded.)
6. Discard the 20ml syringe containing the purged supernatant.
7. Attach a 20ml syringe containing 10-15ml on non-ionic contrast medium to the 3 way-stopcock and inject the contents into the 30ml syringe containing the doxorubicin loaded HepaSphere/QuadraSphere. This will yield a 50/50 ratio of contrast medium to embolic volume. (If greater radio opacity is desired, increase the amount of non-ionic contrast medium added to the syringe.)
8. Invert the 30ml syringe containing the non-ionic contrast media and doxorubicin loaded HepaSphere/QuadraSphere several times to disperse the contents.
9. Connect the 30ml syringe to a 3 way-stopcock.
10. Two options for embolic aliquot sequestering for injection may be utilized:
 - a. **Option 1:** Connect the 3 way-stopcock to the 30ml syringe containing the doxorubicin loaded HepaSphere/QuadraSphere to the infusion micro catheter and utilize a 3ml syringe for injection via the open port of the 3 way-stopcock.
 - b. **Option 2:** Serial aliquots of the doxorubicin loaded HepaSphere/QuadraSphere may be sequestered from the 30ml syringe into a 3ml injection syringe via a 3 way-stop cock that is not attached to the infusion catheter. The 3ml syringe containing the sequestered aliquot may be independently attached to the infusion microcatheter and injected.

Embolization Process:

Procedural Endpoint: Targeted drug dose delivery with associated stasis to all identified pedicles supplying the tumor (s).

1. Use a Microcatheter with a minimum inner diameter of .024”.
2. Conduct delivery of the doxorubicin loaded HepaSphere/QuadraSphere under fluoroscopic guidance.
3. Verify antegrade peri catheter flow prior to embolization/delivery of HepaSphere/QuadraSphere. (Pericatheter flow is required to deliver the HepaSphere/QuadraSphere to the tumor vasculature. Any presence of vasospasm or hindrance of antegrade flow in the vessel preferentially feeding the tumor should be resolved prior to delivery of the spheres.)
4. Utilize an injection syringe no larger than 3ml for delivery of the doxorubicin loaded HepaSphere/QuadraSphere.

5. Inject the sequestered aliquot of doxorubicin loaded HepaSphere/QuadraSphere in a non forceful, pulsatile manner to avoid and minimize the potential for reflux. Delivery of the doxorubicin loaded HepaSphere/QuadraSphere must be done slowly, at a rate of approximately 1-2cc per minute.
6. The angiographic endpoint during delivery of the doxorubicin loaded micro spheres is stasis in the selected feeding pedicle (2nd and 3rd order branches). *Multiple super selective catheterizations may be necessary to achieve complete tumor infusion.
7. If stasis in the feeding pedicle is encountered while delivering the doxorubicin loaded microspheres, wait five minutes then perform a selective angiogram performed after the five minute wait to verify the arrest of antegrade flow. (Secondary distribution of the microspheres may occur lending to continued antegrade flow.)
8. If stasis has not been achieved in the selected feeding pedicle and the target dose of doxorubicin loaded HepaSphere/QuadraSphere has been administered, use supplemental bland embolization utilizing non- doxorubicin loaded HepaSphere/QuadraSphere to arrest antegrade flow.
 - a. Perform hydration of the HepaSphere/QuadraSphere for supplemental bland embolization in accordance with the product instructions for use (IFU).
 - i. Hydrate the HepaSphere/QuadraSphere in the prepackaged vial with 10ml of 0.9% normal saline
 - ii. Wait 10 minutes
 - iii. Extract spheres from vial utilizing a 20ml syringe with a 20g needle attached
 - iv. Add 10ml of non-ionic contrast medium to the hydrated spheres
9. For multifocal disease, treat the target lesion first, followed by treatment of any secondary lesions.

APPENDIX D

Procedural Guidelines for Solubilizing Doxorubicin for Conventional TACE (cTACE)

Supplies:

- 3 x doxorubicin 50mg powder vial (total dose doxorubicin 150mg)
- 20G needles
- 5 x 20ml syringes
- 15ml of 0.9% normal saline
- 2 x syringe caps

Procedure:

****Prepare in Biohazard Hood****

1. Reconstitute each doxorubicin 50mg vial with 5ml of 0.9% normal saline
*This process will yield three vials of doxorubicin 50mg/5ml each
2. Divide the reconstituted dose into 2-20ml syringes

Syringe A: Aspirate 7.5ml of reconstituted doxorubicin into a 20ml syringe

Syringe B: Aspirate 7.5ml of reconstituted doxorubicin into a 20ml syringe

3. Cap each 20ml syringe containing 75mg of doxorubicin in 7.5ml of 0.9% saline and dispense to interventional radiology.

APPENDIX E

Procedural Guidelines for Conventional TACE (cTACE)

Arteriography:

1. Perform routine diagnostic visceral angiography (Aorta, SMA ,Celiac) with delayed portal venous phase.
2. Conduct selective angiography (PHA, LHA, RHA, etc). Perform complete hepatic arteriography, selecting and mapping any accessory or replaced artery as identified.
3. After delineation of the arterial anatomy, advance a coaxial 3 Fr micro-catheter with a minimum inner diameter of 0.024" through the guiding catheter.
4. Serially sub-select and map the smallest arterial branches supplying identified tumors.
5. Multiple super selective catheterizations may be necessary.

Catheter placement and aberrant anatomy:

1. Prior to cTACE, in cases where substantial or clinically relevant arterial portal venous shunting is present, embolize any identified shunts in a manner that occludes the shunt but preserves the hypervascularity of the tumor.
2. Patients with unifocal tumors should undergo selective chemoembolization, in which a 3 Fr microcatheter is placed selectively into a second or third-order branch off the right or left hepatic artery in closer proximity to the tumor.
3. In cases where selective catheterization of second or third-order branches off the right or left hepatic artery is prohibited, segmental catheter position is acceptable.
4. Lobar embolization should be performed only if selective or segmental embolization is not an option.

Drug and Embolic Preparation prior to injection:

1. The doxorubicin solubilized in 0.9% normal saline will be dispensed in 2-20ml syringes. Each syringe will contain doxorubicin 75mg/7.5ml.
2. Transfer the contents of each 20ml syringe containing the solubilized doxorubicin into the operative field via a 3-way stopcock and into a 20ml syringe.
3. After passing the contents into the operative field, connect each of the 20ml syringes to an open port on a 3 way-stopcock.

4. Attach a 20ml syringe containing up to 10ml of ethiodized oil to the open port on the 3 way-stopcock attached to the syringe containing the doxorubicin.
5. Emulsify the doxorubicin and oil mixture with a back a forth motion between the 2 syringes via the 3 way- stopcock.
6. After emulsifying the oil/doxorubicin mixture, sequester the entire volume of the emulsification in one of the 20ml syringes attached to the stopcock and discard the empty syringe.
7. Repeat steps 4-6 for the remaining 20ml syringe containing the solubilized doxorubicin. A procedural maximum of 20ml of ethiodized oil is permitted.
8. Two options for embolic aliquot sequestering for injection may be utilized:
 - c. **Option 1:** Connect a 3 way-stopcock to the 20ml syringe containing the oil/doxorubicin emulsion to the infusion micro catheter and utilize a 3ml syringe for injection via the open port of the 3 way-stopcock.
 - d. **Option 2:** Serial aliquots of the oil/doxorubicin emulsion may be sequestered from the 20ml syringe into a 3ml injection syringe via a 3 way-stopcock that is not attached to the infusion catheter. The 3ml syringe containing the sequestered aliquot may be independently attached to the infusion microcatheter and injected.

Embolization Process:

Procedural Endpoint: Target drug dose delivery with associated angiographic stasis to all identified pedicles supplying the tumor (s).

1. Use a microcatheter with a minimum inner diameter of .024”.
2. Conduct delivery of the oil/doxorubicin emulsion under fluoroscopic guidance.
3. Verify antegrade pericatheter flow prior to embolization/delivery of the oil/doxorubicin emulsion. (Pericatheter flow is required to deliver the oil/doxorubicin emulsion to the tumor vasculature. Any presence of vasospasm or hindrance of antegrade flow in the vessel preferentially feeding the tumor should be resolved prior to delivery of the emulsion.)
4. Utilize an injection syringe no larger than 3ml for delivery of the oil/doxorubicin emulsion.
5. Inject the sequestered aliquot of oil/doxorubicin emulsion in a non forceful, pulsatile manner to avoid and minimize the potential for reflux.
6. The angiographic endpoint during delivery of the oil/doxorubicin emulsion is stasis in the selected feeding pedicle (2nd and 3rd order branches). *Multiple super selective catheterizations may be necessary to achieve complete tumor infusion.

7. If stasis in the feeding pedicle is encountered while delivering the oil/doxorubicin emulsion, wait five minutes then perform a selective angiogram after the five minute wait to verify the arrest of antegrade flow. (Secondary distribution of the oil/doxorubicin emulsion may occur lending to continued antegrade flow.)
8. If stasis has not been achieved in the selected feeding pedicle, and the target dose of oil/doxorubicin emulsion has been administered, use non spherical polyvinyl alcohol (nsPVA) in the size range of >100um and <500um to arrest antegrade flow (stasis) in the feeding pedicle.
9. For multifocal disease, treat the target lesion first, followed by treatment of any secondary lesions.

